7.3. Protocol Safety Review Team

The PSRT will review all AEs (including reportable AEs) on a regular and expedited basis as needed. In addition, the PSRT will review aggregate safety data reports on a weekly basis until 4 weeks after all participants have completed the vaccination, then the safety reviews will occur monthly. The PSRT will review SAEs that potentially meet study pause criteria on an expedited basis and will decide if the study should be paused for participant safety purposes. This team includes the following: Principal Investigator or designee, Associate Investigators, Protocol Consultants, DoD Research Monitor, sponsor IND Medical Officer or designee, and other VRC Representatives. Additional participants could include study personnel and senior clinical research nursing staff. A quorum is established with the PI or designee, one AI or designee, and IND Medical Officer or their designee. If the DoD Research Monitor is not available for the PSRT call, they must provide input by email and then be immediately emailed the outcome of the PSRT discussion.

In addition to the regular and expedited meetings, the PSRT will conduct the following three interim safety data reviews to assess whether or not the safety data meet criteria for moving on to the next stage of the study.

Review for Continuation of 1×10^{10} PU Dose of VRC- MARADC087-00-VP: No more than 1 participant per day will be enrolled into the group for the first 3 participants. When the first 3 participants who have received the 1×10^{10} PU dose have completed post vaccination follow up through at least the “Study Day 7” visit, an interim safety data review will be conducted by the PSRT. Enrollment of the remaining 17 participants in the group may proceed if the PSRT assesses the data as safe to continue.

Review for Dose Escalation to 1×10^{11} PU Dose of VRC- MARADC087-00-VP: When the last participant who has received the 1×10^{10} PU dose has completed post vaccination follow up through at least the “Study Day 7” visit, an interim safety data review will be conducted by the

PSRT. If the safety data support proceeding to the 1×10^{11} dose, then enrollment of Group 2 will begin.

Review for Continuation of 1×10^{11} PU Dose of VRC- MARADC087-00-VP: No more than 1 participant per day will be enrolled into the group for the first 3 participants. When the first 3 participants who have received the 1×10^{11} PU dose have completed post vaccination follow up through at least the “Study Day 7” visit, an interim safety data review will be conducted by the PSRT. Enrollment of the remaining 17 participants in the group may proceed if the PSRT assesses the data as safe to continue.

After each of these interim safety reviews, the IRB and VRC will be provided with documentation of the safety review and notification of the plan.

7.4. Criteria for Study Pause or Termination

The Principal Investigator will closely monitor and analyze study data as they become available and will make determinations regarding the presence and severity of adverse events. The administration of study injections and new enrollments will be paused and the IND Sponsor will be promptly notified according to the following criteria:

- **One** (or more) participant experiences a **SAE** that is assessed as possibly, probably or definitely related to study agent, or
- **Two** (or more) participants experience the same **Grade 3 or 4** adverse event assessed as possibly, probably or definitely related to study agent.

Plan for Review of Pauses and Resuming Rules:

The study injections and enrollments would resume only if review of the adverse events that caused the pause resulted in a recommendation to permit further study injections and study enrollments. The reviews to make this decision will occur as follows:

Pauses for SAEs: The IND Sponsor and PSRT will conduct the review, consult with the FDA, if needed, and make the decision to resume, amend or close the study for any SAEs that meet the criteria for pausing the study. The FDA will be notified of any SAE pause review.

Pauses for Grade 3 or 4 AEs: The IND Sponsor and PSRT will conduct the review and make the decision to resume, amend or close the study for the Grade 3 or 4 events that meet the criteria for pausing the study. As part of the pause review, the reviewers will also advise on whether the study needs to be paused again for any subsequent Grade 3 or 4 event of the same type. The FDA will be notified of all Grade 3/4 pause reviews.

When indicated, safety data reports and changes in study status (study pauses) will be submitted to the IRB in accordance with Section 12.2 and institutional policy.

7.5. Reporting Serious and Unexpected Adverse Events

7.5.1. Study Reporting Period for SAEs

The protocol-defined expedited event reporting period is 48 weeks after study agent administration (study completion) or discontinuation of the participant from study participation for any reason. After the end of the protocol-defined SAE Reporting Period stated above, sites must report suspected unexpected serious adverse reactions (SUSARs) if the study site staff

becomes aware of the event from a participant on a passive basis (i.e., from publicly available information).

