3.0 ENDPOINTS

3.1. Primary Endpoints: Safety

Assessment of product safety will include clinical observation and monitoring of clinical chemistry and hematology parameters. Safety will be closely monitored after injection and evaluated through 48 weeks after the study injection. The following parameters will be assessed for all study groups:

- Occurrence of solicited local reactogenicity signs and symptoms for 7 days following the vaccination
- Occurrence of solicited systemic reactogenicity signs and symptoms for 7 days following the vaccination
- Change from baseline for safety laboratory measures
- Occurrence of adverse events of all severities through 28 days after the study injection
- Occurrence of serious adverse events and new chronic medical conditions through the last study visit

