4.0 STUDY DESIGN AND METHODS

This is a Phase I open-label, dose escalation clinical trial to evaluate the safety, tolerability and immunogenicity of cAd3-vectored vaccines for Marburg WT GP in healthy adults. The study will be conducted at the WRAIR CTC in Silver Spring, Maryland, USA.

Twenty participants will be enrolled in each of the two dosage groups for cAd3-Marburg. The study will begin with enrollment of 3 participants into Group 1. After at least 7 days of follow-up for the first 3 vaccinated participants, an interim safety review will occur before enrollment of additional participants into the group. If no safety issues are identified, an additional 17 participants will be enrolled to complete Group 1. When there is a minimum of seven days of follow-up safety data from the last enrolled participant in Group 1, an interim safety review will occur. Once no safety issues are identified, enrollment of participants into the next dose level will begin with the enrollment of 3 participants. After at least 7 days of follow-up for the first 3 vaccinated participants in Group 2, an interim safety review will occur before the enrollment of additional participants into Group 2. If no safety issues are identified, an additional 17 participants will be enrolled to complete Group 2. For the first 3 participants in each group, only one participant per day will be enrolled.

Study agent administration will be on Day 0. The study includes daily review of any new safety data by a study clinician and weekly review of safety data by the Protocol Safety Review Team (PSRT). The staged enrollment plan and plan for interim safety reviews (Section 7.3) applies to both Group 1 and Group 2. The interim safety reviews will be conducted by the PSRT.

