5.5. Early Discontinuation or Withdrawal of Study Participants

A participant may be discontinued from protocol participation for the following reasons:

1. Repeated failure to comply with protocol requirements
2. Participant requests withdrawal
3. Participant develops a medical condition that is a contraindication to continuing study participation
4. The PI assesses that it is not in the best interest of the participant to continue participation in the study

Each participant has the right to withdraw from the study at any time for any reason without affecting the right to treatment by the investigator. The investigator should make an attempt to contact participants who did not return for scheduled visits or follow-up. Although the participant is not obliged to give reason(s) for withdrawing prematurely, the investigator should make a reasonable effort to ascertain the reason(s) while fully respecting the participant's rights.

Any participant who withdraws consent will not have any further data collected after consent has been withdrawn. However, samples and data that were collected prior to a participant's withdrawal of consent will be used/included in sample and data analysis.

The investigator also has the right to withdraw a participant, e.g., because of worsening health status, intercurrent illness, or other event, which makes further follow-up impossible.

As this is a phase I open label study, participants may be replaced if they did not receive the study injection. A volunteer who has been assessed as eligible for the study through screening will take the place of the participant that did not receive the study injection. The participant who did not receive the study injection will not count toward the total participants enrolled in the study.

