5.6. Management of Participants Who Become Pregnant

Pregnant women and women who plan to become pregnant during the first 24 weeks after study vaccine administration are excluded from enrollment. If a participant becomes pregnant during the course of the study, they will continue to be followed for the remainder of the study period for safety. Blood draws will be conducted for safety purposes only. The PI or designated associate investigator will be responsible for reporting any pregnancy. New pregnancies will be reviewed weekly in aggregate with other safety data and forwarded as necessary to IRBs and study sponsors.

If a participant becomes pregnant within 24 weeks after the study vaccination, every effort will be made to remain in contact with the pregnant participant to record the outcome of pregnancy for the study database. Pregnancy outcomes will be recorded via a standardized pregnancy CRF. Information documented on this form will include date of last menstrual period, date pregnancy confirmed, history of complications during prior pregnancies (such as congenital abnormalities or spontaneous abortions). A separate pregnancy outcome CRF will be completed for the outcome of the pregnancy including date of termination or delivery, any complications of pregnancy, the gender, weight, presence of any congenital abnormalities, APGAR score, other complications of delivery and status of the child.

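### No active collection of new SAEs or new chronic conditions to Week 48 is specified for a vaccinated participant whom the investigator discontinues, yet that participant stays in the safety denominator

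*Combined protocol and SAP*

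**What the plan says.** Four parts of the protocol bear on this.

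- **Reporting period.** Section 7.5.1 gives the expedited reporting period as "48 weeks after study agent administration (study completion) or discontinuation of the participant from study participation for any reason". After it closes, "sites must report suspected unexpected serious adverse reactions (SUSARs) if the study site staff" learn of the event passively. Nothing more is required from that point.
- **Endpoint.** Section 3.1 states the aim: "Safety will be closely monitored after injection and evaluated through 48 weeks after the study injection". The relevant primary endpoint in the same section is "Occurrence of serious adverse events and new chronic medical conditions through the last study visit". Section 5.2.1 sets the same end point for recording these events in the database. Section 7.2 limits recording after Day 28 to SAEs and to new chronic conditions needing ongoing management.
- **Discontinuation.** Section 5.5 lists four reasons: repeated non-compliance, the participant's own request, a medical condition ("Participant develops a medical condition that is a contraindication to continuing study participation"), and the PI's judgment of best interest. Separately, the investigator may withdraw a participant "because of worsening health status, intercurrent illness, or other event, which makes further follow-up impossible". Only withdrawal of consent expressly stops further data collection.
- **Dosing and analysis set.** Section 4.0 says "Study agent administration will be on Day 0", and there is no second dose. Section 8.3 analyses all vaccinated participants. Section 5.5 allows replacement only of someone who was not injected.

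**The concern.** After Day 0 there is no further product to withhold. Continued participation means visits, safety assessments and blood draws, so discontinuing a vaccinated participant removes only observation. Reasons 1, 3 and 4 in Section 5.5 (non-compliance, medical condition, best interest) can all apply to someone who has not withdrawn consent and could still be reached by telephone.

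Section 8.2.1 summarises safety as the proportion of participants with an event. If a participant is no longer asked about new events but stays in the denominator, any later event lowers the numerator and nothing else. When the reason for leaving is the participant's health, the loss may be related to the outcome. The missing-at-random statement in Section 8.3.3 concerns immunogenicity responses, and no rule covers incomplete safety follow-up.

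At stake are a primary safety endpoint in groups of 20, where one event changes the result visibly, and possibly the pause rule in Section 7.4, which a single related SAE triggers.

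**Working it through.** **1. Is there any active contact after discontinuation?**

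| Provision | What it covers | New, separate events after discontinuation? |
|---|---|---|
| 7.5.1, first sentence | SAE reporting until Week 48 or discontinuation | No, the period has ended |
| 7.5.1, second sentence | SUSARs that staff learn of passively | Only if related, unexpected and by chance known; not other SAEs or chronic conditions |
| 7.2 | AEs followed until resolved or stable | No, only events already open |
| 5.5 | Attempts to contact participants who did not return | Does not address participants the investigator removes |
| 5.6 (pregnancy) | "they will continue to be followed for the remainder of the study period for safety" | Yes, but the participant is not discontinued |
| 5.7 (incarceration) | Visits suspended, safety contact allowed | Safety contact is kept during the suspension |
| Appendix 1 | Visits 01 to 07 | No early-termination visit or later safety contact |

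No provision supplies active collection to Week 48 for a vaccinated participant discontinued under reasons 1, 3 or 4. If the last study visit in Section 3.1 means the participant's own last visit, the endpoint window closes early. If it means the scheduled Week 48 visit, the window stays open but nothing fills it.

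**2. Reproduce the plan's precision figures (Table 4, Section 8.2.1).** The Clopper-Pearson limits for x events in n are:

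- lower = Beta quantile 0.025 with parameters (x, n − x + 1), or 0 if x = 0
- upper = Beta quantile 0.975 with parameters (x + 1, n − x), which is 1 − 0.025^(1/n) when x = 0

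Results:

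- 0/20: upper = 1 − 0.025^(1/20) = 16.84% (Table 4: 16.8%)
- 0/40: upper = 1 − 0.025^(1/40) = 8.81% (Table 4: 8.8%)
- 1/20: 0.13% to 24.87% (Table 4: 0.1% to 24.9%)

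The plan's figures are right. As statements about 48-week risk, they assume that all 20 or 40 participants are fully observed for SAEs.

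**3. What incomplete observation could do.** The documents give no dropout rate, so d, the number discontinued in a group of 20, is an assumption. Suppose no SAE is recorded.

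| d | Reported, 0/20 | Upper limit, fully observed only: 1 − 0.025^(1/(20 − d)) | If each of the d had one uncaptured SAE |
|---|---|---|---|
| 1 | 0% (0%-16.8%) | 17.6% | 1/20 = 5% (0.1%-24.9%) |
| 2 | 0% (0%-16.8%) | 18.5% | 2/20 = 10% (1.2%-31.7%) |
| 3 | 0% (0%-16.8%) | 19.5% | 3/20 = 15% (3.2%-37.9%) |

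The last column is a worst case. It also requires that none of the d had a qualifying event before leaving.

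**4. Observation time lost per participant**, for assumed discontinuation times:

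- Week 8: (48 − 8)/48 = 40/48 = 83%
- Week 24: (48 − 24)/48 = 24/48 = 50%

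**5. Pause rule.** Under Section 7.3, Group 2 may open once the last Group 1 participant has completed the Day 7 visit and the review supports it. A discontinued Group 1 participant could therefore have a related SAE while Group 2 is being dosed. No accrual duration is given, so how long that overlap would last cannot be stated.

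**The case against.** The other side has several good points.

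- **The participant does not drop out of the endpoint.** A reader might infer that someone removed for illness leaves the SAE analysis altogether. Section 8.3 keeps all vaccinated participants, and events before discontinuation count. This stands.
- **The condition prompting removal may already count.** It is recorded as an AE through Day 28, and afterwards if it is an SAE or a new chronic condition needing ongoing management. If so, the participant is already a case under that endpoint bullet. This stands, and it is why the 0/20 illustration needs a participant with no earlier qualifying event, or SAEs tabulated on their own.
- **Worsening of that condition is covered.** Section 7.2 follows open AEs without excepting discontinued participants. This stands, and it narrows the gap to new, separate events.
- **Reporting does not stop entirely.** Passively learned SUSARs remain reportable. This stands, but the endpoint also counts unrelated or expected SAEs and new chronic conditions, which that clause does not reach.
- **Discontinuation is permissive.** The investigator's separate right to withdraw for worsening health is tied to follow-up being impossible. This stands for that sentence. Listed reasons 1, 3 and 4 carry no such limit.
- **Section 7.5.1 concerns expedited reporting, and pregnancy is not an exact precedent.** Both are fair. Endpoint capture is set in Sections 3.1, 5.2.1 and 7.2, so amending 7.5.1 alone would not be enough.

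The consent forms were not available to check, so what participants are told about contact after removal is unknown.

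**Conclusion.** The point holds in a limited form. For a vaccinated participant discontinued without consent withdrawal, the plan specifies no active collection of new SAEs or new chronic conditions to Week 48, and it does not say how incomplete safety follow-up is shown in the analysis. The loss can be informative and, with the denominator fixed, can only lower the observed proportion.

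The size cannot be estimated: no dropout rate is given and the affected subgroup may be empty. Under the stated assumption of one uncaptured SAE in a participant with no earlier qualifying event, a group result of 5% (0.1%-24.9%) would be reported as 0% (0%-16.8%).

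Two stronger readings are tempting but unsupported. One is that follow-up ends just when a late event is most likely; the documents contain no data on the timing or hazard of events after discontinuation. The other is that the pause rule would certainly be missed. It could be, but only for a related SAE that nobody reports, and only while injections or enrolment continue.

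This is a design weakness and not an arithmetic error. It merits correction because the correction is cheap.

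**What to change.** Reconcile Sections 3.1, 5.2.1, 5.5, 7.2 and 7.5.1 as follows.

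1. State that SAEs and new chronic conditions are collected until Week 48, withdrawal of consent, death or loss to follow-up, whichever comes first. Use this cut-off in the endpoint definition, the recording rules and the reporting period.
2. In Section 5.5, ask a vaccinated participant who is discontinued without withdrawing consent to accept telephone safety contacts at the remaining visit dates, without research blood draws.
3. In Section 8.3.2, report for each group how many participants completed 48-week SAE follow-up, beside the all-vaccinated proportion.

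The cost is protocol and consent wording plus a few telephone calls. No clinic visits or blood volume are added, and the sample size and Table 4 are unchanged.

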7.5.2. Expedited Reporting of SAEs to the IND Sponsor

All SAEs must be reported and submitted by the clinical site on an expedited basis to the IND sponsor, VRC/NIAID/NIH. In addition, any event, regardless of severity, which in the judgment of an investigator represents a serious adverse event, may be reported on an expedited basis.

An investigator will communicate the initial SAE report within 24 hours of site awareness of occurrence to the IND sponsor throughout the study reporting time period. Notification of SAEs will be sent via email to the PSRT, which includes the IND Medical Officer.

A written report by investigator should be submitted to the IND Sponsor within 3 working days. In order for the IND Sponsor to comply with regulations mandating sponsor notification of specified SAEs to the FDA within 7 or 15 calendar days, the investigator must submit additional information as soon as it is available.

7.5.3. IND Sponsor Reporting to the FDA

The IND Sponsor is responsible for making the determination of which SAEs are SUSARs that meet criteria for expedited reporting as defined in 21 CFR 312.32.

- *Suspected adverse reaction* means any adverse event for which there is a reasonable possibility that the drug caused the adverse event.
- *Unexpected Adverse Event* means an AE that is not listed in the Investigator's Brochure or is not listed at the specificity or severity that has been observed.

The IND Sponsor will submit written IND Safety Reports to the FDA in accordance with 21 CFR 312.32 as soon as possible and, in no event, later than 15 calendar days after determining that the information qualifies for reporting. Per FDA guidance, the IND Sponsor will submit any unexpected fatal or life-threatening suspected adverse reactions to the FDA as a written IND Safety Report as soon as possible, but no later than 7 calendar days following the IND Sponsor's initial receipt of the information.

The IND Sponsor is responsible for providing copies of IND Safety Reports for submission to the WRAIR IRB.

7.5.4. Reporting Serious and Unexpected Adverse Events to WRAIR and HPRO

All SAEs that are considered related or possibly related, and all deaths, will be promptly (within 48 hours) reported to the WRAIR IRB. Written reports will be submitted within 10 working days to the WRAIR IRB. The WRAIR HSPB will report SAEs to USAMRMC ORP HRPO as per SOP UWZ-C-636.

Follow up reports will be submitted as additional information becomes available. A summary of the non-serious adverse events and SAEs (both related and unrelated) that occurred during the reporting period will be included in the continuing review report (CRR) to the WRAIR IRB.

IND Safety Reports from the VRC will be simultaneously submitted to the FDA via the IND sponsor and to the WRAIR IRB via the PI/designee. WRAIR HSPB will forward to USAMRMC ORP HRPO as per SOP UWZ-C-636.

The WRAIR IRB will also be immediately notified if any study pause criteria are met. WRAIR HSPB will forward to USAMRMC ORP HRPO as per SOP UWZ-C-636.

7.6. Unanticipated Problems Reporting

All non-serious unanticipated problems (events not involving risk to participants or others) will be reported in the continuing review report to the WRAIR IRB.

All serious unanticipated problems involving risk to subjects or others (UPIRTSOs) (including but not limited to disclosure of personal health information, breach of confidentiality, destruction or loss of study records, unaccounted for study drug, etc.) should be promptly (within 48 hours) reported to the WRAIR IRB by [contact]) or by email ([contact]) and to the IND sponsor via email. The Principal Investigator will then submit a written report within 10 working days to the WRAIR IRB at the following address: Walter Reed Army Institute of Research, ATTN: Human Subject Protection Branch (HSPB), [name], [name] 20910.

Follow up reports should be submitted as soon as additional information becomes available. A summary of the serious unanticipated problems will also be included in the continuing review report submitted to the WRAIR IRB. The WRAIR HSPB will report unanticipated problems to the USAMRMC ORP HRPO as per UWZ-C-636.

The DoD medical monitor should also review the unanticipated events and provide an independent assessment for submission to the sponsor and WRAIR IRB (as a local medical research monitor's report). WRAIR HSPB will report these summaries to USAMRMC ORP HRPO.

